12.6.4 Safety Evaluation

Safety variables monitored in this study include: AEs; vital signs (systolic and diastolic blood pressure, pulse rate, respiratory rate); spirometry; ECG data; concomitant medication, clinical chemistry, hematology, urine analysis safety panel, BMI, physical examination, respiratory symptoms (cough assessment).

The primary analysis of Safety parameters will be conducted on the Safety Population as described in Section 12.1.3 “**Descriptive Statistics**”.

12.6.4.1 Safety Reporting

An exposure emergent AE is defined as an AE that occurs after first product use or that is present prior to first product use and becomes more severe after first product use. All other AEs will not be summarized but provided in listings only.

All AEs occurring from the time of signing of informed consent will be recorded electronically. However, during the screening period (prior to first product use), only study related AEs will be summarized. The AE listings will include all AEs captured in the database at any time during the study (including those from subjects who were not in the Safety Population).

AEs reported for subjects that have a first product use, but were not randomized will be summarized in a separate group: “Exposed but not randomized”.

Partial dates will not be imputed, but assumptions will be made as follows to assign to product-emergent or not:

Date information	Assign as
Partial date, e.g. --May2012, or -----2011. If month/year is the same as, or later than the month and/or year of Screening.	Product-emergent
Partial date, e.g. --May2012, or -----2011. If month and/or year is earlier than the month and/or year of Screening.	Not product-emergent

12.6.4.2 Adverse Events

12.6.4.2.1 All Adverse Events

All AE tables will be presented by actual exposure.

A general summary table of AEs will be presented including:

- The number of events and the number and percentage of subjects reporting at least one AE.
- The number of events and the number and percentage of subjects reporting at least one study product –related AE, broken down by product relatedness (related to THS 2.2 / CC) and expectedness (expected for THS 2.2 / CC).
- The number of events and the number and percentage of subjects reporting at least one AE broken down by severity including each subject only once with his worst severity.
- The number of events and the number and percentage of subjects reporting at least one SAE.
- The number of events and the number and percentage of subjects reporting at least one AE leading to any action taken, broken down by action taken related to the product (product use interrupted, product use reduced, product use stopped, not applicable, none), treatment given (yes, no), study discontinuation, other action taken.
- The number of events and the number and percentage of subjects reporting at least one AE related to study procedure.

Additional summary tables of AEs will be presented with a breakdown of the number of events, as well as the number and percentage of subjects reporting each AE, categorized by system organ class (SOC) and preferred term (PT) coded according to the Medical Dictionary for Regulatory Activities (MedDRA) dictionary (version 16.0):

- The number of events and the number and percentage of subjects reporting at least one AE.
- The number of events and the number and percentage of subjects with at least one AE related to product exposure and expectedness for investigational product (IP; THS 2.2 or CC).
- The number of events and the number and percentage of subjects with at least one AE leading to product discontinuation or reduction.
- The number of events and the number and percentage of subjects with at least one AE leading to study discontinuation.
- The number of events and the number and percentage of subjects with at least one AE related to study procedure.
- The number of events and the number and percentage of subjects with at least one AE by severity (mild, moderate, severe).

If a subject has more than one occurrence of the same AE, the subject will be counted only once within a PT with the worst occurrence based on the presentation (e.g., for presentation by severity = severe, for presentation by relationship = related). Missing information on the intensity of AE will be counted as severe.

The data will be presented in the below outputs, the TFL number refers to the TFL number in the accompanying TFL shell document:

TFL number	Title
TABLES	
15.2.6.1	Summary of Adverse Events – Safety Population
15.2.6.2.1	Summary of Adverse Events by System Organ Class and Preferred Term – Safety Population
15.2.6.2.2	Summary of Adverse Events by System Organ Class – Safety Population
15.2.6.2.3	Summary of Adverse Events by Preferred Term – Safety Population
15.2.6.3	Summary of Adverse Events by System Organ Class, Preferred Term and Relationship to Study Product Exposure for Investigational Product (THS 2.2 or CC) and Expectedness – Safety Population
15.2.6.4	Summary of Adverse Events Leading to Investigational Product (THS 2.2 or CC) Discontinuation or Reduction by System Organ Class and Preferred Term – Safety Population
15.2.6.5	Summary of Adverse Events Leading to Study Discontinuation by System Organ Class and Preferred Term – Safety Population
15.2.6.6	Summary of Adverse Events Related to Study Procedure by System Organ Class and Preferred Term – Safety Population
15.2.6.7	Summary of Adverse Events by System Organ Class, Preferred Term and Severity – Safety Population
15.2.6.8	Summary of Serious Adverse Events – Safety Population
LISTINGS	
15.3.6.1.1	Listing of Adverse Events

12.6.4.2.2 Serious Adverse Events (Including Deaths)

A general summary table of SAEs will be presented using the same approach of AEs (see Section 12.6.4.2 “Adverse Events”), and including the number of events and the number and percentage of subjects reporting at least one SAE broken down by seriousness criteria (fatal, life-threatening, requires hospitalization, results in disability/incapacity, congenital anomaly/birth defect).

SAEs will also be listed in a separate listing by actual exposure.

The data will be presented in the below outputs, the TFL number refers to the TFL number in the accompanying TFL shell document:

TFL number	Title
TABLES	
15.2.6.8	Summary of Serious Adverse Events – Safety Population
15.2.6.9	Summary of Serious Adverse Events by System Organ Class and Preferred Term – Safety Population
LISTINGS	
15.3.6.1.2	Listing of Serious Adverse Events

12.6.4.2.3 Adverse Events Leading to Discontinuation

Summaries will be presented for AEs leading to withdrawal, by actual exposure as described in Section 12.6.4.2 “Adverse Events”,

AEs leading to withdrawal will also be listed in a separate listing by actual exposure.

The data will be presented in the below outputs, the TFL number refers to the TFL number in the accompanying TFL shell document:

TFL number	Title
TABLES	
15.2.6.5	Summary of Adverse Events Leading to Study Discontinuation by System Organ Class and Preferred Term – Safety Population
LISTINGS	
15.3.6.1.3	Listing of Adverse Events Leading to Study Discontinuation

12.6.4.2.4 Laboratory Abnormalities

Laboratory abnormality data will be listed ordered by actual exposure, subject, parameter and time point. Details related to the toxicity grading of laboratory abnormalities are available in Section 12.6.4.4 “Clinical Laboratory Evaluation”.

The data will be presented in the below outputs, the TFL number refers to the TFL number in the accompanying TFL shell document:

TFL number	Title
LISTINGS	
15.3.6.4	Listing of Clinical Chemistry Data Shift, Changes from Baseline and CTCAE grades
15.3.6.5	Listing of Hematology Data Shift, Changes from Baseline and CTCAE grades
15.3.6.6	Listing of Urinalysis Data Shift, Changes from Baseline and CTCAE grades

12.6.4.3 THS 2.2 Device Events

All events relating to the device type will be listed for each subject, including event description, device type the event relates to, severity of event, AE relationship, proposed solution and onset/stop dates/times. Device events will be classified according to **C54451/Medical_Device_Problem_Codes_FDA_CDRH**.

A summary table of device events will be presented by actual exposure, including:

- Number of device events and the number and percentage of subjects reporting at least one device event.
- Number of device events and the number and percentage of subjects categorized by severity of device event (minor, major).
- Number of device events and the number and percentage of subjects categorized by AE relationship (related, not related).
- Number of device events and the number and percentage of subjects categorized by event description (Cigarette Holder (CH) stops heating, CH does not charge, CH led blinking red, Smoking experience does not start, electronic malfunction, other).

Device events and inventory will be listed by actual exposure. Data collected during Screening will be listed but not summarized.

The data will be presented in the below outputs, the TFL number refers to the TFL number in the accompanying TFL shell document:

TFL number	Title
TABLES	
15.2.6.9	Summary of THS 2.2 Device Events and Malfunctions – Safety Population
LISTINGS	
15.3.6.2	Listing of THS 2.2 Device Events and Malfunctions

12.6.4.4 Clinical Laboratory Evaluation

Table 20 below lists the hematology, clinical chemistry and urine analysis parameters to be assessed in this study.

Table 20: List of Laboratory Safety Parameters

Hematology	Clinical chemistry	Urine analysis
Haematocrit	Albumin	pH
Haemoglobin	Total protein	Bilirubin
Mean corpuscular haemoglobin	Alkaline phosphatase	Glucose
Mean corpuscular haemoglobinconcentration	Alanine aminotransferase	Nitrite
Mean corpuscular volume	Aspartate aminotransferase	Red blood cell traces
Platelet count	Blood urea nitrogen	Protein
Red blood cell count	Creatinine	Specific gravity
White blood cell (WBC) count	Gamma-glutamyltransferase	
Differential WBC count:	Fasting glucose	
• Neutrophils	Lactate dehydrogenase	
• Basophils	Potassium	
• Eosinophils	Sodium	
• Lymphocytes	Total bilirubin	
• Monocytes	Direct bilirubin	
	Total cholesterol	
	Triglycerides	

Any clinical safety laboratory test result that is outside of the normal reference range will be reviewed by the Investigator and assessed for its clinical relevance. If the Investigator considers the abnormal result to be of clinical relevance, then it must be recorded as a concomitant disease at Screening, or if not present at Screening, as an AE during the study. If the condition worsens from screening to after product-use it will be recorded as an AE.

The grading scheme used in the Common Terminology Criteria for Adverse Events and Common Toxicity Criteria [CTCAE] (version 4.03) will be used by the Investigator to assess abnormal laboratory results. These CTCAE grades will be derived programmatically in the creation of the datasets.

Laboratory data will be summarized at Screening, Day 0 and at Day of Discharge (Day 6 or day of withdrawal), together with changes from baseline. These data will also be listed. The number and percentage of subjects with normal results, high/low results and abnormal clinical result (as judged by the PI) will be tabulated for laboratory parameters.

Listings for the clinical laboratory data will include the following information: normal/high/low (with respect to the reference range), abnormal clinically relevant (as judged by the PI), the PI comments, the change from baseline and the CTCAE grade. Only CTCAE grades greater than zero will be presented.

The data will be presented in the below outputs, the TFL number refers to the TFL number in the accompanying TFL shell document:

TFL number	Title
TABLES	
15.2.6.12	Summary of Clinical Chemistry Parameters – Safety Population
15.2.6.13	Summary of Hematology Parameters – Safety Population
15.2.6.14	Summary of Urinalysis Parameters – Safety Population
LISTINGS	
15.3.6.4	Listing of Clinical Chemistry Data, Shift, Changes from Baseline and CTCAE grades
15.3.6.5	Listing of Hematology Data Shift, Changes from Baseline and CTCAE grades
15.3.6.6	Listing of Urinalysis Data Shift, Changes from Baseline and CTCAE grades

12.6.4.5 Vital Signs, Physical Findings and Other Observations Related to Safety

12.6.4.5.1 Prior and Concomitant Medication

Prior medication is defined as any medication that started and ended prior to Screening. Concomitant medication is defined as any medication starting on or after Screening. Medications that started prior to Screening and are ongoing at Screening are considered as concomitant.

All medications will be listed by actual exposure using PT and Anatomical Therapeutic and Chemical (ATC) codes (World Health Organisation-Drug Dictionary Enhanced [WHO-DDE] Q1 2012). A flag will be presented on the listing indicating whether the medication is prior or concomitant. Partial dates will not be imputed, but assumptions will be made as follows to assign to either prior or concomitant:

Date information	Assign as
Missing stop date	Concomitant
Partial date, e.g. --May2012, or -----2011. If month/year is the same as, or later than the month and/or year of Screening.	Concomitant
Partial date, e.g. --May2012, or -----2011. If month and/or year is earlier than the month and/or year of Screening.	Prior

Prior and concomitant medications will be listed by actual exposure. Concomitant medications will be summarized for the Safety Population showing the number and percent of subjects who used the medication at least once by actual exposure and by ATC 1st and 2nd levels and preferred drug name. Listings will be provided by arm and will display original dates (no imputation).

The data will be presented in the below outputs, the TFL number refers to the TFL number in the accompanying TFL shell document:

TFL number	Title
TABLES	
15.2.6.10.1	Summary of Prior Medication by Anatomical Therapeutic Classes (ATC) 1 and 2 – Safety Population
15.2.6.10.2	Summary of Prior Medication by Preferred Drug Name – Safety Population
15.2.6.11.1	Summary of Concomitant Medication by Anatomical Therapeutic Classes (ATC) 1 and 2 – Safety Population
15.2.6.11.2	Summary of Concomitant Medication by Preferred Drug Name – Safety Population
LISTINGS	
15.3.6.3	Listing of Prior and Concomitant Medication

12.6.4.5.2 Physical Examination

Physical examination data recorded at the Screening visit, Admission (Day -2) and at the day of Discharge (Day 6 or at the day of withdrawal for withdrawn subjects) will be listed by actual exposure. Subject's data with abnormal and abnormal clinically relevant physical examination findings will be flagged. The number and percent of subjects with normal, abnormal and abnormal clinically significant results will be tabulated by body systems at Screening, Admission and day of Discharge.

Body weight recorded at Admission and day of Discharge; and body height recorded at the Screening visit will also be listed together with BMI. Descriptive statistics of body weight, body height and BMI (BMI will also be categorized as shown in Section 7.5 "Categorical Variables"), at Admission and Day of Discharge will be presented.

The data will be presented in the below outputs, the TFL number refers to the TFL number in the accompanying TFL shell document:

TFL number	Title
TABLES	
15.2.6.18	Summary of Weight and BMI Measurements – Safety Population
LISTINGS	
15.3.6.10	Listing of Physical Examination Findings, Shift and Changes from Baseline

12.6.4.5.3 Vital Signs

Systolic and diastolic blood pressure, pulse rate and respiratory rate values measured during the study will be listed by study visit, including low/normal/high results. Assessment after baseline (last assessment prior to 06:29 AM on Day 1) will include change from baseline.

Descriptive statistics will be presented for systolic and diastolic blood pressure, pulse rate and respiratory rate at baseline, and on every subsequent day of the confinement period by actual exposure for each study day. Vital signs data will be summarized together with changes from baseline.

The data will be presented in the below outputs, the TFL number refers to the TFL number in the accompanying TFL shell document:

TFL number	Title
TABLES	
15.2.6.15	Summary of Vital Signs – Safety Population
LISTINGS	
15.3.6.7	Listing of Vital Signs Data and Changes from Baseline

12.6.4.5.4 Spirometry

Spirometry parameters assessed during the study include:

- Measured forced expiratory volume in 1 second (FEV₁)
- Measured forced vital capacity (FVC)
- FEV₁/FVC
- Predicted FEV₁
- Percent of predicted FEV₁ (% pred)
- Predicted FVC
- Percent of predicted FVC (% pred)
- Measurement interpretation (categories: normal, abnormal, abnormal clinically significant)

The above data are collected at Screening, Day 0, and Day of Discharge (Day 6 or day of withdrawal). At Screening, data are collected prior and post-bronchodilator, also including the brand (trade) name and dose of the bronchodilator.

Spirometry predicted values will not be standardized to the NHANES III predicted set as planned in the protocol. Predicted FEV₁ and FVC will be calculated according to the formula recommended by the Japanese Respiratory Society (Sasaki H, Nakamura M et al., 2001) for Japanese population.

Spirometry data values and normality evaluation will be listed by actual exposure and study day. Assessments performed after baseline (Day 0) will be listed together with change from baseline and shift in normality. Spirometry data from subjects who had relevant clinical findings will be highlighted in listings.

Descriptive statistics will be presented for FEV₁(L), FEV₁ (% pred), FVC(L), FVC(% pred), and FEV₁/FVC at baseline, and Discharge by actual exposure, and overall. Spirometry data will be summarized together with changes from baseline (pre-bronchodilator), and the number and percentage of subjects with

normal/abnormal/abnormal clinically significant results. The post-bronchodilator data will not be included in these summaries, they will only be listed.

The data will be presented in the below outputs, the TFL number refers to the TFL number in the accompanying TFL shell document:

TFL number	Title
TABLES	
15.2.6.17	Summary of Spirometry Results – Safety Population
LISTINGS	
15.3.6.8	Listing of Spirometry Data and Changes from Baseline

12.6.4.5.5 Electrocardiogram

The ECG data will be obtained directly from the 12-lead ECG traces, i.e. not centrally read. These data include the PR, QT, and QT interval corrected using Bazett's formula (QTcB) intervals; QRS duration; and heart rate; and normality evaluation (normal, abnormal, clinically relevant, together with any PMI comments to the abnormality). In addition the QTcF value will be presented.

The baseline for the ECG data will be the Screening value.

ECG data values and normality evaluations will be listed by actual exposure and study day (Screening and Day 6) together with changes from baseline and shift in normality. ECG data from subjects which had significant clinical findings will be highlighted in listings.

Descriptive statistics will be presented for ECG data at baseline, and Day 6 by actual exposure. ECG data will be summarized together with changes from baseline, and the number and percentage of subjects with normal/abnormal/abnormal clinically significant results.

The data will be presented in the below outputs, the TFL number refers to the TFL number in the accompanying TFL shell document:

TFL number	Title
TABLES	
15.2.6.16	Summary of ECG Measurements – Safety Population
LISTINGS	
15.3.6.9	Listing of ECG Data and Changes from Baseline

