6.6 Restrictions

6.6.1 Smoking Restrictions and Restrictions to the Smoking Abstinence Arm

To avoid cross contamination between the 3 study arms, subjects must use THS 2.2 and CC must in separate rooms and subjects allocated to the SA arm should not have access to the smoking rooms. All precautions should be taken to remove any temptation to smoke for subjects who are randomized to the SA study arm.

In the THS 2.2 and SA arms, subjects will not be allowed to smoke any CC or use any nicotine/tobacco containing products (including NRT) from Day 1 (06:30 AM) until Day 5 (11:00 PM). In the CC arm, subjects will not be allowed to use the THS 2.2, any nicotine/tobacco containing products and other CC than collected to the site by the subject.

During the confinement period, smoking will generally only be allowed during the designated smoking times, from 06:30 AM to 11:00 PM. Smokers will not have free access to their CC or THS 2.2; these will be dispensed by the study site collaborator individually as described in Section 6.5.1.

Smoking will not be allowed during assessments on the Admission Day at the discretion of the site. Smoking is also not allowed from Day 5, 11:00 PM until the spirometry has been performed on Day 6.

In general, the performance of scheduled procedures has priority over the wish of a subject to smoke. However, this is different at Day 5 due to the assessment of the nicotine profile. If the subject wants to smoke at Day 5 around the time of the blood draw, he/she should inhale/smoke first and the blood will be drawn after the tobacco stick/cigarette has been inhaled/smoked.

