7.4.8 Vital signs

Systolic and diastolic blood pressure, pulse rate and respiratory rate will be measured at the Screening Visit, at Admission (Day -2), and in the morning of every day of the confinement period (i.e. Days -1 to 6). All measurements will be made after the subject has rested for at least 5 minutes in a supine position.

For every measurement, it will be documented if the subject has smoked within 15 minutes prior to the measurement.

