7.4.9.2 Electrocardiogram

An ECG will be recorded at Screening, and at Day 6. Electrocardiogram testing will be performed as per the site's local practice. A standard 12-lead ECG will be recorded after the subject has rested for at least 10 minutes in a supine position.

The following parameters will be documented: heart rate, PR interval, QRS interval, QT interval and QT interval corrected by the ECG machine according to Bazett's formula. Every ECG has to be assessed as normal, abnormal – clinically not relevant, or abnormal – clinically relevant. A diagnosis has to be provided on the eCRF for all ECGs assessed as abnormal – clinically relevant. All ECG print-outs will be interpreted by a qualified physician. Any print-outs of ECGs on thermo-sensitive paper must be photocopied and stapled together for inclusion in the Source Documents.

Confidentiality statement: Data and information contained in this document are considered to constitute trade secrets and confidential commercial information, and the legal protections provided to such trade secrets and confidential information are hereby claimed under the provisions of applicable law. No part of this document may be publicly disclosed without the written consent of Philip Morris Products S.A.

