9.1 Screening Visit

The screening Visit will be performed within 4 weeks (Day -30 to Day -3) prior to admission (Day -2). Subjects will attend the investigational site in at least 10-hour fasting state for clinical laboratory to be assessed. Table 6 shows the assessments that will be performed at the Screening Visit. First, the ICF should be given to the subject. When/if the ICF is signed, the other screening procedures can be performed in the order deemed most practical. While it is recommended to complete as much screening procedures as possible in one day, it is permissible to complete those over more than one day. Smoking is allowed during screening.

Table 6. Time Schedule – Screening Visit

Time	Blood sample	Procedures	Additional information
Start of procedure		Screening	
		ICF for study participation and ICFs for both bio-bankings	
		Advice on the risk of smoking and debriefing	
		Demographic data collected	

Confidentiality statement: Data and information contained in this document are considered to constitute trade secrets and confidential commercial information, and the legal protections provided to such trade secrets and confidential information are hereby claimed under the provisions of applicable law. No part of this document may be publicly disclosed without the written consent of Philip Morris Products S.A.

Time	Blood sample	Procedures	Additional information
Start of procedure		Screening	
		Identification of current CC brand	
		Medical history/concomitant disease	
		Prior medication (4 weeks prior to Screening Visit) and concomitant medication	
		Smoking history	
		Willingness to quit smoking within the next 3 months and readiness to abstain from smoking for at least 5 days	
		Vital signs (blood pressure, pulse rate, respiratory rate)	At least 5 minutes in supine position prior to measurement
	√	Clinical laboratory parameters (hematology, urine analysis, clinical chemistry)	To be done at least 10 hours after fasting
	√	HIV, hepatitis B and C	
		Physical examination and height, weight, calculation of BMI	
		THS 2.2 product demonstration	
		Chest X-ray (if not performed 6 months prior to Screening Visit)	
		Urine drug screen	
		Urine cotinine screening test	
		Alcohol breath test screen	
		Urine pregnancy test (all females only)	
		Fagerström Test for Nicotine Dependence (FTND)	
		Spirometry first without short-acting bronchodilator then with.	To be done at least 1 hour after smoking

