		ECG	At least 10 minutes in supine position prior to recording
		AE/SAE recording	If the Screening Visit is performed on two separate days the AE/SAE questions will be asked again
		Inclusion/exclusion criteria	

Confidentiality statement: Data and information contained in this document are considered to constitute trade secrets and confidential commercial information, and the legal protections provided to such trade secrets and confidential information are hereby claimed under the provisions of applicable law. No part of this document may be publicly disclosed without the written consent of Philip Morris Products S.A.

Time	Blood sample	Procedures	Additional information
Start of procedure		Screening	

Abbreviations: AE = adverse event; BMI = body mass index; CC = conventional cigarette(s); ECG = electrocardiogram; HIV = human immunodeficiency virus; SAE = serious adverse event; THS = tobacco heating system.

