12.1.2 Definitions for Statistical Data Analysis

In general, baseline is the last available time-point prior to Day 1, 06:30 AM.

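### Smoking state is not standardised at either ECG, so within-arm changes in heart rate and QTcB from Screening to Day 6 can partly reflect smoking and not the assigned product

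*SAP*

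**What the plan says.** Protocol 7.4.9.2 sets the ECG schedule: "An ECG will be recorded at Screening, and at Day 6". The general rule in Protocol 12.1.2 is "In general, baseline is the last available time-point prior to Day 1, 06:30 AM", and since Screening is the only pre-exposure tracing, SAP 12.6.4.5.5 follows it: "The baseline for the ECG data will be the Screening value". The SAP then gives ECG values at baseline and Day 6 by actual exposure, changes from baseline, and counts of normal, abnormal and clinically significant results. It presents both QTcB and QTcF.

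At Screening, Protocol 9.1 says "Smoking is allowed during screening", although Protocol 6.2 lets the site restrict smoking during the visit's procedures. Table 6 attaches one condition to the ECG: "At least 10 minutes in supine position prior to recording". In the same table, spirometry must be at least 1 hour after smoking.

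For Day 6, Protocol 6.6.1 says: "Smoking is also not allowed from Day 5, 11:00 PM until the spirometry has been performed on Day 6". Protocol 4.1 allows CC after that. In Table 15 the ECG and vital signs are scheduled only as before discharge, with a supine rest, whereas CYP2A6, cough, MNWS and spirometry all carry a before-smoking condition.

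For vital signs, Protocol 7.4.8 adds: "For every measurement, it will be documented if the subject has smoked within 15 minutes prior to the measurement". No such record is specified for the ECG.

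**The concern.** ECG is a named safety endpoint, and Day 6 supplies its only post-exposure tracing. If smoking state can differ between the two tracings, a change in heart rate, or in a QT interval corrected by Bazett's formula, need not be an effect of the assigned product. The CC arm never changes product, yet it could show a change for this reason alone, and the same component would sit inside the THS 2.2 and SA changes. In addition, a THS 2.2 or SA subject who smokes a CC after spirometry and before the ECG contributes a post-exposure tracing that follows the reference product. The sponsor controlled smoking for spirometry at both visits but not for the ECG.

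**Working it through.** The plan gives no figure to reproduce here. The check compares the scheduling rules, then illustrates size with the SAP's own formulas.

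**Smoking state at each tracing**

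| | Screening ECG | Day 6 ECG |
|---|---|---|
| Product use beforehand | Allowed; site may restrict during procedures (Protocol 9.1, 6.2) | Barred from 11:00 PM on Day 5 until spirometry, then CC allowed (6.6.1, 4.1) |
| Condition on the ECG | Supine rest only (Table 6) | Before discharge, supine rest (Table 15) |
| Recent smoking recorded for the ECG | Not specified | Not specified |

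Neither column fixes the smoking state. A Day 6 tracing made before the first cigarette follows at least 11:00 PM to 06:29 AM = 7 h 29 min without product if it is made when the 24-hour urine collection ends; Table 15 gives no clock time for spirometry or ECG. A tracing made after spirometry can follow a CC. Screening runs from Day -30 to Day -3, so the tracings are 6 - (-3) = 9 to 6 - (-30) = 36 days apart.

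**Size, by assumption.** SAP section 7 gives QTcB = QT / (60/HR)^(1/2) and QTcF = QT / (60/HR)^(1/3). Hence QTcB = QTcF x (HR/60)^(1/6). The documents give no acute effect of smoking on heart rate, so 5 to 10 bpm is assumed. With QTcF held at 400 ms:

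- 60 bpm: QTcB = 400 ms
- 65 bpm: 400 x (65/60)^(1/6) = 405.4 ms
- 70 bpm: 400 x (70/60)^(1/6) = 410.4 ms

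For QTcF from 380 to 420 ms and starting rates of 65 to 75 bpm, a 5 bpm fall lowers QTcB by 4.5 to 5.6 ms and a 10 bpm fall by 9.3 to 11.7 ms. A rise moves it the other way. QTcF is unchanged by construction.

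**Between arms.** Let s be a shift common to all arms and e the true product effect. The THS 2.2 change is e + s, the CC change is s, and the difference is e, so s cancels. If fractions p1 and p2 of two arms smoke a CC before the Day 6 ECG, and this moves heart rate by d, the difference is off by (p1 - p2) x d. With an assumed p1 - p2 = 0.5, that is 0.5 x 5 = 2.5 to 0.5 x 10 = 5 bpm, and about 0.5 x 5.4 = 2.7 to 0.5 x 10.4 = 5.2 ms in QTcB.

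**Vital signs.** The baseline is the Day 0 reading, taken from 10:00 to 11:30 AM. Days 1 to 4 use the same window, during product use. The Day 5 window also opens at 10:00 AM, though Table 14 prints its end as 11:30 PM. Only the Day 6 reading has a different, unspecified relation to smoking.

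**The case against.** A reader might infer a fixed contrast between a Screening tracing made while smoking and an abstinent Day 6 tracing, and so expect the CC arm to show a fall in heart rate and QTcB. The documents do not support that. The site may restrict smoking during Screening procedures, and a Day 6 tracing may follow a CC, so the direction is unknown.

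A reader might also infer that the randomised comparison is biased. Screening precedes randomisation, and the overnight ban and the Day 6 ECG rules are the same in every arm, with CC as a concurrent control. Only unequal CC use before the Day 6 ECG could bias it. That is plausible, since SA subjects may wish to stay abstinent (Protocol 6.2.5) and Day 6 nicotine sampling times differ by arm, but nothing shows that it occurs.

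Nor is it right that the SAP reports within-arm change alone. Day 6 values and abnormality counts by exposure allow a direct reading across arms. QTcF limits dependence on Bazett's correction. For vital signs, "Vital signs data will be summarized together with changes from baseline" covers every confinement day, and Days 1 to 4 are time-matched to baseline. The recent-smoking record falls under the general listing rule in SAP 12.1, although the vital-signs section gives it no role.

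All of this stands and narrows the point. It leaves the uncontrolled smoking state at both ECGs, and the possibility that the only post-exposure tracing follows a CC.

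**Conclusion.** The concern holds in a limited form. Smoking state is not standardised at either ECG, so within-arm changes in heart rate and QTcB can partly reflect it, in a direction the documents do not determine. The illustrative size, about 5 to 11 ms of QTcB for 5 to 10 bpm, rests on an assumed heart-rate effect and on constant QTcF; it shows Bazett's rate dependence and is not an estimate of what this study would show. Between-arm comparisons are at risk only through unequal CC use on Day 6 before the tracing. The effect is confined to descriptive safety summaries: the two ECGs and, for vital signs, the Day 6 reading. No primary or confirmatory result depends on it.

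**What to change.** - **Protocol Table 15, 7.4.9.2 and 7.4.8:** give the Day 6 ECG and vital signs the before-smoking condition that four other Day 6 items already carry.
- **SAP 12.6.4.5.5:** add descriptive Day 6 differences, THS 2.2 minus CC and THS 2.2 minus SA, with 95% CI, for heart rate and QTcF, adjusted for the Screening value. State that ECG changes are to be read against the concurrent CC arm and not as within-arm change alone.
- **SAP listings:** flag any Day 6 tracing taken after a CC. Protocol 6.5.1 requires dispense and return times on each confinement day, so the log may supply this if Day 6 dispensing and ECG times were captured. Flag such tracings but do not drop them, since this smoking happens after randomisation.

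Extending the 1-hour spirometry interval to the Screening ECG would not cure the mismatch: it would set at least 1 hour at Screening against about 7.5 hours on Day 6.

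The cost is a small constraint on the order of Day 6 procedures and one added table, with no new visit or procedure. A before-smoking Day 6 ECG will not capture acute on-product effects. If fieldwork is complete, the SAP changes can still be made.
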